5.3 Subject Enrollment

Before subjects begin participation in any study-specific activities/procedures, Amgen requires a copy of the site's written Institutional Review Board/Independent Ethics Committee (IRB/IEC) approval of the protocol, informed consent form, and all other subject information and/or recruitment material, if applicable (see Section 11.3).

Protocol Number: 20200392

Date: 28 April 2022 Page 49 of 149

The subject must personally sign and date the IRB/IEC and Amgen approved informed consent before commencement of study-specific procedures.

A subject is considered enrolled when the investigator decides that the subject has met all eligibility criteria. The investigator is to document this decision and date, in the subject's medical record and in/on the Subject Enrollment Case Report Form (CRF).

Each subject who enters into the screening period for the study 14 days prior to day 1 receives a unique subject identification number before any study-related activities/procedures are performed. The subject identification number will be assigned manually. This number will be used to identify the subject throughout the clinical study and must be used on all study documentation related to that subject.

The subject identification number must remain constant throughout the entire clinical study; it must not be changed after initial assignment, including if a subject is rescreened.

5.4 Screen Failures

Screen failures are defined as subjects who consent to participate in the clinical study but are not subsequently enrolled in the study. A minimal set of screen failure information will be collected that includes demography, screen failure details, eligibility criteria, medical history, prior and concomitant (if subject experienced a serious adverse event) therapies, and any serious adverse events.

Individuals who do not meet the criteria for participation in this study (screen failure) may be rescreened. Refer to Section 8.1.1.

6. Study Intervention

Study intervention is defined as any investigational product(s), non-investigational product(s), placebo, combination product(s), or medical device(s) intended to be administered to a study subject according to the study protocol.

Note that in several countries, investigational product and non-investigational product are referred to as investigational medicinal product and non-investigational medicinal product, respectively.

Protocol Number: 20200392

Date: 28 April 2022 Page 50 of 149

A summary of the dosing and administration of each treatment is shown in Table 6-1 below.

- 6.1 Study Interventions Administered
- 6.1.1 Investigational Products

Protocol Number: 20200392

Date: 28 April 2022 Page 51 of 149

Protocol Number: 20200392

Date: 28 April 2022 Page 52 of 149

Protocol Number: 20200392

Date: 28 April 2022 Page 53 of 149

6.1.2 Non-investigational Products

The non-investigational product used in this study (azacitidine) may be considered investigational in some countries. Refer to regional prescribing information for full details.

Decisions regarding the AMG 176 lead-in dosing period regimen, lead-in period starting dose, dosing increments, will be made by DLRT and communicated to the IRB/IEC, as appropriate (see Section 11.3).

Azacitidine will be administered at 75 mg/m² IV over approximately 15 minutes or via subcutaneous injection daily for 7 days on days 1 to 7 of each treatment cycle. Treatment cycles will begin on day 1 of each new azacitidine cycle.

Azacitidine will be dosed based on actual body weight. However, at the treating physician's discretion, an adjusted body weight may be used, if the actual body weight is greater than 40% over the ideal body weight.

 $Adjusted\ body\ weight \\ = 0.4(actual\ body\ weight-ideal\ body\ weight) + ideal\ body\ weight$

The patient's baseline body weight will be used throughout treatment with consideration given to update the dosing weight for a weight change of greater than 10%.

After cycle 1, azacitidine may be subsequently administered at any of the Houston Area Locations (HALs) or at the patients' local oncologists' offices, and a schedule of 7 azacitidine doses within 9 days is allowed due to possible weekend closure of local offices. Patients will receive one course every 4 to 8 weeks; however, delays of more than 8 weeks may be allowed if determined by the investigator to be in the best interest of the patient after discussion with the PI and the discussion documented in the patient's medical record.

Azacitidine will be obtained from commercial sources. Please refer to the FDA prescribing information for azacitidine for further details.

6.1.3 Medical Devices

There are no investigational devices in this study.

Other non-investigational medical devices may be used in the conduct of this study as part of standard care.

Protocol Number: 20200392

Date: 28 April 2022 Page 54 of 149

Non-Amgen non-investigational medical devices (eg, syringes, sterile needles), that are commercially available are not usually provided or reimbursed by Amgen (except, for example, if required by local regulation). The investigator will be responsible for obtaining supplies of these devices.

6.1.4 Other Protocol-required Therapies

All other protocol-required therapies including, allopurinol, that are commercially available are not provided or reimbursed by Amgen (except if required by local regulation). The investigator will be responsible for obtaining supplies of these protocol-required therapies.

6.1.4.1 Tumor Lysis Prophylaxis (All Subjects)

There is a potential for TLS in subjects, affected by hematologic malignancies especially in those with bulky disease, elevated pretreatment Lactate Dehydrogenase (LDH) levels, elevated leukocyte count, renal dysfunction, and dehydration. To mitigate the risk of TLS, AMG 176 lead-in dosing (see Section 6.1.1) will be used and TLS prophylaxis must be initiated in all subjects prior to all lead-in dosing of AMG 176 and prior to all subsequent dose escalations (ie, first dose on the targeted cohort dose level). Prior to administering these doses, all electrolyte values (including potassium, uric acid, phosphorous, calcium, and creatinine) should be reviewed and must be within normal range. However, LDH is not mandatory.

All other protocol-required therapies including, allopurinol, that are commercially available are not provided or reimbursed by Amgen (except if required by local regulation). The investigator will be responsible for obtaining supplies of these protocol-required therapies.

All subjects will be hospitalized to monitor for TLS and all TLS monitoring assessments will be performed as outlined in the Schedule of Activities (see Section 1.3).

The management recommendations below focus on the minimum initial responses required. If a diagnosis of TLS is established, ongoing intensive monitoring and multi-disciplinary management will be conducted per institutional protocols (Coiffier et al, 2008; Cairo et al, 2004).

Tumor lysis syndrome prophylaxis includes:

 Allopurinol or equivalent should be used to reduce uric acid level. This should be initiated at least 72 hours prior to dosing. Treatment may need to be continued for up to 5 weeks. Other agents to reduce uric acid level, such as rasburicase,

Protocol Number: 20200392

Date: 28 April 2022 Page 55 of 149

may be used per principal investigator discretion and the institutional guidelines. Dosing per institutional guidelines.

- Hospitalization and monitoring, beginning the night before AMG 176 administration until at least 24 hours post-first AMG 176 dose.
- IV hydration must be started the night before AMG 176 administration and to be continued until at least 24 hours post—dose during hospitalization as clinically tolerated (refer to Section 11.9.3 for more details about the level of IV hydration required).
- Monitoring of electrolyte values is required prior to dosing anytime a dose is higher than one previously given to the subject. This will include at the following times:
 - Prior to the week 1, day 1 dose.
 - Prior to each dose during the lead-in period.
 - Prior to the initial dosing at the target dose level.
- Prior to administering these doses, all electrolyte values (including LDH, potassium, uric acid, phosphorus, calcium, and creatinine) must be reviewed and within normal range (samples must be drawn within 24 hours prior to dosing of AMG 176). The investigator's decision to proceed with AMG 176 treatment initiation will be based on these laboratory values.

Within the first 24 hours after either the first dose or dose escalation, if any laboratory criteria for TLS are met, no additional AMG 176 doses should be administered until resolution. A rapidly rising serum potassium is a medical emergency.

Prophylactic dose reductions for potassium, phosphorus and/or uric acid values at the high end of normal range should be considered.

If the potassium, uric acid, inorganic phosphate and/or creatinine values are higher than the normal range or the calcium is lower or higher than the normal range, this (these) value(s) can be approved following a discussion between the Amgen Medical Monitor and investigator.

On the AMG 176 dosing days chemistry labs must be performed pre-dose (within 4 hours before AMG 176 administration), 2, 4, 8, 12, and 24 hours after the start of AMG 176 infusion. Pre-dose labs will be used as baseline to assess potential electrolytes abnormalities occurring post AMG 176 administration. These labs must be reviewed in real time by the investigator.

All 24-hour laboratory assessments may be taken \pm 2 hours, if necessary.

Monitor for signs and symptoms of TLS (eg, fever, chills, tachycardia, nausea, vomiting, diarrhea, diaphoresis, hypotension, muscle aches, weakness, paresthesias, mental status changes, confusion, and seizures). If any clinical features are observed, recheck potassium, phosphorus, uric acid, calcium, and creatinine within 1 hour.

Additional information on the management recommendations of laboratory abnormalities can be found in Section 11.2.

 Nephrology (or acute dialysis service) consultation should be considered on admission (based on investigator discretion) for hospitalized subjects per

Protocol Number: 20200392

Date: 28 April 2022 Page 56 of 149

institutional guidelines to ensure emergency dialysis is available and the appropriate staff is aware and prepared.

6.1.5 Other Intervention Procedures

There are no other treatment procedures in this protocol.

6.1.6 Product Complaints

A product complaint is any written, electronic or oral communication that alleges deficiencies related to the identity, quality, durability, reliability, safety, effectiveness, or performance of a drug, combination product, or device after it is released for distribution to market or clinic by either (1) Amgen or (2) distributors or partners for whom Amgen manufactures the material. This includes all components distributed with the drug, such as packaging drug containers, delivery systems, labeling, and inserts.

This includes any investigational/non-investigational product provisioned and/or repackaged/modified by Amgen: AMG 176.

Any product complaint(s) associated with an investigational product or non-investigational product supplied by Amgen are to be reported.

6.1.7 Excluded Treatments, Medical Devices, and/or Procedures During Study Period

The following medications and/or therapies should not be administered within the timeframes specified prior to enrollment or during the study (unless otherwise specified below):

- Allogenic stem cell transplant.
- Autologous stem cell transplant.
- Anti-tumor therapy (chemotherapy, antibody therapy, molecular targeted therapy, retinoid therapy, or investigational agent or procedures); concurrent use of bisphosphonates or denosumab for bone loss are permitted.
- Treatment with medications known to cause QTc interval prolongation unless approved by the Amgen Medical Team.
- Any live vaccine therapies used for the prevention of infectious disease.
- Any major surgery or radiotherapy unless agreed upon by Amgen and investigator.
- Over the counter medication(s) that was not reviewed and approved by the principal investigator and the Amgen medical monitor.
- Herbal medicines (eg, St. John's wort) that were not reviewed and approved by the principal investigator and the Amgen medical monitor.

The use of certain medications and illicit drugs within 5 half-lives or 28 days, whichever is shorter prior to the first dose of study drug and for the duration of the trial will not be

Protocol Number: 20200392

Date: 28 April 2022 Page 57 of 149

allowed. If a prohibited medication is required for single use (such as for a procedure) while study drug is held, the Amgen medical monitor can approve such use.

The following medications or non-drug therapies are prohibited:

 Use of known strong inhibitors of CYP3A4/P-gp such as ketoconazole, itraconazole, HIV protease inhibitors, nefazodone, cyclosporine, erythromycin, clindamycin, tetracycline, and clarithromycin within the 14 days or 5 half-lives (whichever is longer) or products containing grapefruit, Seville oranges, or St. John's wort within 7 days, prior to enrollment.

- Use of known CYP3A4 sensitive substrates with a narrow therapeutic window (such as pimozide, and sirolimus) within 5 half-lives of the drug or its major active metabolite, whichever is longer, following the last dose of the drug prior to receiving the first dose of AMG 176. Refer to prescribing information for concomitant medications.
- Use of known OATP1B1 and/or OATP1B3 substrates with a narrow therapeutic window within 5 half-lives of the drug or its major active metabolite, whichever is longer, following the last dose of the drug prior to enrollment. Refer to prescribing information for concomitant medications.
- Use of known BCRP substrates with a narrow therapeutic window within 5 half-lives of the drug or its major active metabolite, whichever is longer, following the last dose of the drug prior to enrollment. Refer to prescribing information for concomitant medications.
- Oral contraceptives (either combined or progesterone only), estrogenic vaginal ring/percutaneous contraceptive patches, or implants of levonorgestrel/injectable progesterone is prohibited in this study as it is not known if there is the potential of inhibition/induction of enzymes that affect the metabolism of estrogens and/or progestins.

If use of any other prior or concomitant medication or procedure is in question, please refer to prescribing information and/or consult with the Amgen medical monitor.

There are no prohibited therapies and procedures during the 30-day safety follow-up or the long-term follow-up.

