- Calculated or measured Creatinine Clearance (CrCl) of ≥ 30 mL/minute calculated using the formula of Cockcroft and Gault ([140 Age × Mass kg] / [72 × Creatinine mg/dL]). Multiply result by 0.85 if female.
- 110 Females must be surgically or biologically sterile or postmenopausal (amenorrheic for at least 12 months) or if of childbearing potential, must have a negative serum or urine pregnancy test within 72 hours before the start of the treatment. Female subjects of childbearing potential must agree to use highly effective methods of contraception (see Section 11.5) an adequate method of contraception during treatment and until 3 months after the last treatment.
- Males must be surgically or biologically sterile or agree to use an adequate method of contraception during the study until 3 months after the last treatment.

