- Use of known CYP3A4 sensitive substrates with a narrow therapeutic window within 5 half-lives of the drug or its major active metabolite, whichever is longer, following the last dose of the drug prior to receiving the first dose of AMG 176 unless reviewed and approved by the principal investigator and the Amgen medical monitor prior to enrollment. Written documentation of this review and Amgen acknowledgment is required for subject participation. Refer to prescribing information for any concomitant medications.
- 218 Use of known OATP1B1 and/or OATP1B3 or BCRP substrates with a narrow therapeutic window within 5 half-lives of the drug or its major active metabolite, whichever is longer, following the last dose of the drug prior to enrollment unless reviewed and approved by the principal investigator and the Amgen Medical Monitor prior to enrollment. Written documentation of this review and Amgen acknowledgment is required for subject participation. Refer to prescribing information for any concomitant medications.
- 219 Major surgery within 28 days of enrollment.

Prior/Concurrent Clinical Study Experience

Currently receiving treatment in another investigational device or drug study, or less than 30 days since ending treatment on another investigational device or drug study(ies). Other investigational procedures while participating in this study are excluded.

Diagnostic Assessments

Subjects with elevated cardiac troponin above the manufacturer's 99th percentile upper reference limit for ADVIA Centaur XP TnI assay at screening performed by the central laboratory.

Protocol Number: 20200392

Date: 28 April 2022 Page 48 of 149

Subjects with evidence of recent cardiac injury at screening based on Creatine Kinase-Muscle/Brain (CK-MB), N-Terminal Prohormone of Brain Natriuretic Peptide (NT-pro BNP), and Electrocardiogram (ECG) assessments at screening.

Patient has a white blood cell count > 10×10^9 /L. Hydroxyurea or leukapheresis are permitted to meet this criterion.

Other Exclusions

- Female subjects of childbearing potential unwilling to use highly effective methods of contraception (see Section 11.5) during treatment and for an additional 3 months after the last dose of investigational product.
- Female subjects who are breastfeeding or who plan to breastfeed while on study through 3 months after the last dose of investigational product.

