8.4.6.6 Pregnancy and Lactation

Details of all pregnancies and/or lactation in female subjects will be collected after the start of study treatment and until 3 months after the last dose of investigational product.

Details of all pregnancies and/or lactation in female partners of male subjects will be collected after the start of study treatment and until 4 months after the last dose of investigational product.

Protocol Number: 20200392

Date: 28 April 2022 Page 84 of 149

If a pregnancy is reported, the investigator is to inform Amgen within 24 hours of learning of the pregnancy and/or lactation and is to follow the procedures outlined in Section 11.5. Amgen Global Patient Safety will follow-up with the investigator regarding additional information that may be requested.

Abnormal pregnancy outcomes (eg, spontaneous abortion, fetal death, stillbirth, congenital anomalies, ectopic pregnancy) are considered serious adverse events.

Further details regarding pregnancy and lactation are provided in Section 11.5.

Pregnancy Testing

A highly sensitive (urine or serum) pregnancy test should be completed at screening and within 7 days of initiation of investigational product for females of childbearing potential.

Note: Females who have undergone a bilateral tubal ligation/occlusion should have pregnancy testing per protocol requirements. (If a female subject, or the partner of a male subject, becomes pregnant it must be reported on the Pregnancy Notification Form, see Figure 11-2). Refer to Section 11.5 for contraceptive requirements.

A pregnancy test should be performed should be performed as indicated in the Schedule of Activities (Section 1.3).

Additional on-treatment pregnancy testing may be performed at the investigator's discretion or as required per local laws and regulations.

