11.5 Appendix 5. Contraceptive Guidance and Collection of Pregnancy and Lactation Information

Study-specific contraception requirements for male and females of childbearing potential are outlined in Section 5.2. Contraceptive use and methods should be consistent with local regulations for subjects participating in clinical studies.

Female subjects of childbearing potential should be advised of the pregnancy prevention requirements and the potential risk to the fetus if they become pregnant during treatment and for 3 months after the last dose of protocol-required therapies.

Male subjects should be advised of the pregnancy prevention requirements and the potential risk to the fetus if they father a child during treatment and for 4 months after the last dose of protocol-required therapies.

Definition of Females of Childbearing Potential

A female is considered fertile following menarche and until becoming post-menopausal unless permanently sterile. Permanent sterilization methods include documented hysterectomy, bilateral salpingectomy, and bilateral oophorectomy. Females with documented permanent infertility due to an alternate medical cause (eg, Mullerian agenesis, androgen insensitivity, gonadal dysgenesis), can be considered not of childbearing potential.

Note: Bilateral tubal ligation/occlusion is not considered a permanent sterilization method.

Note: Documentation from the following sources is acceptable to provide confirmation of each sterilization method: 1) review of subject's medical records; 2) subject's medical examination; or 3) subject's medical history interview.

A postmenopausal female is defined as:

- A woman of ≥ 55 years with no menses for 12 months without an alternative medical cause OR
- A woman age < 55 years with no menses for at least 12 months and with a
 follicle-stimulating hormone (FSH) level within the definition of "postmenopausal
 range" for the laboratory involved. In the absence of 12 months of amenorrhea,
 confirmation with more than one FSH measurement is required.

Contraception Methods for Female Subjects

Highly Effective Contraceptive Methods

 Combined (estrogen and progestogen containing) hormonal contraception associated with inhibition of ovulation (oral, intravaginal, or transdermal).

Protocol Number: 20200392

Date: 28 April 2022 Page 120 of 149

 Progestogen-only hormonal contraception associated with inhibition of ovulation (oral, injectable, implantable).

- Intrauterine device (IUD).

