- Intrauterine hormonal-releasing system (IUS).
- Bilateral tubal ligation/occlusion.
- Vasectomized partner (provided that partner is the sole sexual partner of the female subject of childbearing potential and that the vasectomized partner has received medical assessment of the surgical success).
- Sexual abstinence (defined as refraining from heterosexual intercourse during the
 entire period of risk associated with the study treatments; the reliability of sexual
 abstinence must be evaluated in relation to the duration of the trial and the preferred
 and usual lifestyle of the subject).

Contraception Methods for Male Subjects

- Sexual abstinence (defined as refraining from heterosexual intercourse during the
 entire period of risk associated with protocol-required therapies; the reliability of
 sexual abstinence must be evaluated in relation to the duration of the trial and the
 preferred and usual lifestyle of the subject)
- Use a condom during treatment and for an additional 4 months after the last dose of protocol-required therapies.

The female partner should consider using a method of contraception for female subjects stated above (a female condom should not be used because there is a risk of tearing when both partners use a condom).

Note: If the male's sole female partner is of non-childbearing potential or has had a bilateral tubal ligation/occlusion, he is not required to use additional forms of contraception during the study.

Collection of Pregnancy Information

Female Subjects Who Become Pregnant

- Investigator will collect pregnancy information on any female subject who becomes pregnant while taking protocol-required therapies through 3 months after the last dose of investigational product.
- Information will be recorded on the Pregnancy Notification Form (see Figure 11-2).
 The form must be submitted to Amgen Global Patient Safety within 24 hours of the
 site's awareness of a subject's pregnancy. (Note: Sites are not required to provide
 any information on the Pregnancy Notification Form that violates the country or
 regions local privacy laws).

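### Appendix 5 lists oral, ring, patch, injectable and implantable hormonal contraception as highly effective without saying that Section 6.1.7 prohibits these routes (for implants, levonorgestrel only) during AMG 176 treatment

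*Protocol*

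**What the plan says.** Protocol Section 6.1.7 (excluded treatments) states: "Oral contraceptives (either combined or progesterone only), estrogenic vaginal ring/percutaneous contraceptive patches, or implants of levonorgestrel/injectable progesterone is prohibited in this study". It explains that the potential for inhibition or induction of the enzymes that metabolize estrogens and progestins is unknown. The section closes by limiting its own reach: "There are no prohibited therapies and procedures during the 30-day safety follow-up or the long-term follow-up".

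Appendix 5 (Section 11.5), under its heading for highly effective methods in female subjects, has these two entries among seven:

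- "Combined (estrogen and progestogen containing) hormonal contraception associated with inhibition of ovulation (oral, intravaginal, or transdermal"
- "Progestogen-only hormonal contraception associated with inhibition of ovulation (oral, injectable, implantable"

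Neither entry has a caveat, and Appendix 5 does not mention Section 6.1.7. For study-specific requirements it refers to Section 5.2. For male subjects it adds: "The female partner should consider using a method of contraception for female subjects stated above".

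The contraception text elsewhere relies on Appendix 5. Inclusion criterion 110 in Section 5.1 requires highly effective methods and cites Section 11.5. The matching exclusion criterion in Section 5.2 covers "Female subjects of childbearing potential unwilling to use highly effective methods of contraception (see Section 11.5) during treatment". Section 8.4.6.6 says: "Refer to Section 11.5 for contraceptive requirements".

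On duration for men, the male inclusion criterion in Section 5.1 asks for contraception until 3 months after the last treatment. Section 5.2 and Appendix 5 use 4 months.

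**The concern.** A method can be both highly effective and prohibited, so listing it is not wrong in itself. The defect is the missing caveat. Appendix 5 is the list a site will actually use, because every contraception rule for female subjects points there.

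What is at stake is a fetal-risk safeguard during treatment. Section 2.2.2.2 reports that AMG 176 induced CYP3A4 in human hepatocytes and may cause CYP-mediated interactions by inhibition or induction. The ban in 6.1.7 responds to that kind of uncertainty. If a hormonal method's exposure were altered, its reliability could not be assumed. A woman could be enrolled, or could start a method during treatment, in good faith under Appendix 5 while using something the protocol forbids.

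**Working it through.** No arithmetic applies beyond counting, and the plan gives no figure to reproduce. The check sets the two sections side by side and then follows the cross-references.

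**Step 1. Routes in the two hormonal entries of Appendix 5 against Section 6.1.7**

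| Appendix 5 entry | Route | Named in the 6.1.7 ban? |
|---|---|---|
| Combined | Oral | Yes |
| Combined | Intravaginal | Yes (estrogenic ring) |
| Combined | Transdermal | Yes (patch) |
| Progestogen-only | Oral | Yes |
| Progestogen-only | Injectable | Yes |
| Progestogen-only | Implantable | Yes, levonorgestrel implants only |

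Routes listed: 3 + 3 = 6. Routes named in the ban: 6, with the implant restriction noted.

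**Step 2. Methods affected.** Appendix 5 lists seven methods for female subjects: combined hormonal, progestogen-only hormonal, IUD, hormone-releasing intrauterine system, tubal ligation or occlusion, vasectomized partner, and abstinence. The ban names routes in 2 of the 7. The other 7 − 2 = 5 are not named in it, so alternatives remain.

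**Step 3. Cross-references.** Three places on female contraception cite Section 11.5: inclusion criterion 110, the exclusion criterion in 5.2, and Section 8.4.6.6. None cites 6.1.7. Appendix 5 points back to Section 5.2, which points again to 11.5. The loop is closed and never reaches the ban.

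**Step 4. Period of conflict.** Section 6.1.7 lifts its prohibitions in safety and long-term follow-up. The 3 months of contraception required of women after the last dose fall in follow-up, so there is no conflict then. The conflict is confined to treatment.

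**Step 5. Exceptions.** The medical monitor may approve a prohibited medication under 6.1.7 only for single use while study drug is held. That cannot cover ongoing contraception.

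**Step 6. Male duration.** Three months appears in one place, the male inclusion criterion in Section 5.1. Four months appears in four: the male exclusion criteria in Section 5.2, and in Appendix 5 the opening advice, the male methods list, and the text on partners who become pregnant. The 4 months in Section 8.4.6.6 is a window for collecting pregnancy and lactation details, so it is not counted.

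**The case against.** The strongest reply is that other rules already close most of the gap. Section 5.2 excludes anyone using, in the 30 days before enrollment or continuing, a medication that the principal investigator and the sponsor's medical monitor have not both reviewed and approved, with written documentation. A woman already on a pill, ring, patch, injection or implant cannot enter on the site's reading of Appendix 5 alone. After enrollment, Section 6.7.2 limits concomitant treatment by express reference to 6.1.7 and requires any medication to be reported. Concomitant therapies are reviewed on schedule, and pregnancy is tested before each cycle. On this view Appendix 5 only classifies effectiveness, the specific ban governs, and what is missing is a cross-reference. The SAP also reports that the study was terminated early.

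Much of this stands as a limit on reach. The pre-enrollment approval is a real safeguard and works without the site finding 6.1.7. By its wording, though, it does not cover a woman who starts a listed method after enrollment. For her, the limit in 6.7.2 protects only if the reader consults 6.1.7, to which the contraception text does not lead. Pregnancy testing detects a failure and does not prevent it. Nor is Appendix 5 merely a classification: Section 8.4.6.6 treats it as the source of the requirements. Early termination reduces the practical benefit in this trial but does not make the two sections agree.

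The male point can be called a separate and smaller matter. That is fair: the exclusion criteria already impose 4 months on men with a partner of childbearing potential, so the 3-month figure has little practical effect.

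**Conclusion.** The concern holds. Two operative parts of the protocol point in opposite directions on hormonal contraception during AMG 176 treatment, and the contraception cross-references lead only to the permissive one. Two of seven listed methods and all six of their routes are affected, with implants restricted to levonorgestrel on the wording of 6.1.7.

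Reach is small. The conflict covers the treatment period only, Section 2.2.1 gives a median age at diagnosis of about 70 years, the medication rules protect in part, and SAP Section 3.1 states that Part 2 did not enroll. This is a correction that should be made, not one on which the trial's conclusions depend. The conclusion assumes that the closing sentence of 6.1.7 lifts the contraceptive ban in follow-up, as it reads. The male 3-versus-4-month mismatch is a minor wording error.

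**What to change.** Keep both hormonal entries in Appendix 5 and mark them as not permitted for female subjects during AMG 176 treatment, with a reference to Section 6.1.7 and its levonorgestrel wording for implants. Do not delete them: they are not prohibited in follow-up, and the list also serves female partners of male subjects. A reference to 6.1.7 in the female criteria of Sections 5.1 and 5.2 would help but is optional.

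In the same amendment, change the male inclusion criterion in Section 5.1 from 3 to 4 months.

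The cost is one caveat and one number, with no effect on endpoints, sample size or analysis. Given the early termination, much of the value may lie in the record and in any reuse of this text.
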